7.3 Laboratory tests

Laboratory analyses are based on data received from the central laboratory. Laboratory data will be converted into SI units. Unless noted otherwise, summaries and listings will include scheduled, re-test, and unscheduled assessments.

Descriptive summary statistics for each scheduled visit (re-test excluded) will be provided for observed values and change from baseline in both hematology and blood chemistry laboratory parameters.

The main laboratory parameters will be displayed graphically using boxplots considering only scheduled visit (re-test and unscheduled assessments excluded) and will be grouped (i.e., shown in the same panel) as follows:

- Hemoglobin, hematocrit, platelets, leukocytes (white blood cell count)
- Glucose, uric acid, cholesterol, triglycerides
- Total bilirubin, ALT, AST
- ALP, GGT

Marked laboratory abnormalities are defined in the appendix [Section 14.14]. The number (%) of participants with treatment-emergent marked laboratory abnormalities will be tabulated. A subject will be counted only once but may be reported in more than one marked laboratory abnormality criterion of a given parameter. Percentages will be based on the number of participants having at least one post-baseline value for a given parameter.

Shift from baseline to worst value post-baseline based on laboratory normal ranges will be provided for the following laboratory parameters:

- Liver enzymes: ALT, AST, GGT and BILI.
- Lipids: total cholesterol and triglycerides.
- Hematology: hemoglobin, hematocrit, platelets, leukocytes (absolute count), neutrophils (absolute count), lymphocytes (absolute count).

All laboratory data for participants with at least one marked laboratory abnormality during the treatment period will be listed. Any local laboratory data collected will be listed separately.

ACT-539313		Statistical Analysis Plan
ID-082A201	Confidential	for Clinical Study Report
1 April 2022, page 34/60		Version 3
		Doc No D-22 100

Elevated liver parameters during the treatment period will be summarized: the number (%) of study participants meeting the criteria defined below within a given central laboratory sample will be tabulated by treatment group. Percentages will be based on the number of study participants having at least one post-baseline value for all parameters listed below.

- AST or ALT $> 3 \times ULN$
- AST or ALT $> 5 \times ULN$
- AST or ALT $> 10 \times ULN$
- BILI > $2 \times ULN$
- ALP > $1.5 \times ULN$
- (ALT or AST > $3 \times ULN$) and (BILI > $2 \times ULN$)

A summary table for study participants falling into the Hy's Law criteria will be provided [Andrade 2019]. This will include study participants meeting all the following criteria:

- AST or ALT $> 3 \times ULN$
- BILI > $2 \times ULN$
- ALP $< 2 \times ULN$

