#### 5.9.1.3 Liver aminotransferase abnormalities

If ALT or  $AST \ge 3 \times ULN$  and  $< 8 \times ULN$ , a re-test of aminotransferases, total and direct bilirubin, and alkaline phosphatase must be performed within 7 calendar days. If the aminotransferase values return to pre-treatment levels or within normal ranges, study treatment can be continued. If AST or ALT elevation is confirmed, study treatment must be stopped and not re-introduced. Aminotransferases, total and direct bilirubin, and

alkaline phosphatase levels must be monitored at least once every 7 calendar days until values return to pre-treatment levels or within normal ranges.

Study treatment must be stopped, and its reintroduction is not to be considered in the following cases:

- Aminotransferases  $\geq 8 \times ULN$
- Aminotransferases ≥ 3 × ULN and associated clinical symptoms of liver injury, e.g., nausea, vomiting, fever, abdominal pain, jaundice, unusual lethargy or fatigue, flu-like syndrome (arthralgia, myalgia, fever)
- Aminotransferases  $\geq 3 \times ULN$  and associated increase in total bilirubin  $\geq 2 \times ULN$

Aminotransferases, total and direct bilirubin, and alkaline phosphatase levels must be monitored at least once every 7 calendar days after study treatment discontinuation until values return to pre-treatment levels or within normal ranges.

Furthermore, other diagnoses (e.g., viral hepatitis, mononucleosis, toxoplasmosis, cytomegalovirus, alcoholic hepatitis, non-alcoholic steatohepatitis, autoimmune disease) and/or etiologies (e.g., hepatic toxicity of concomitant medication[s] or other substances) should be considered and ruled out by performing the appropriate tests.

All liver aminotransferases abnormalities leading to study treatment discontinuation must be recorded as AEs [see Section 8.1.1].

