#### 7.2.5.4 Clinical laboratory assessments

See schedule of activities [Table 1] for the timing and frequency.

A central laboratory (see central laboratory manual for contact details) will be used for all protocol-mandated laboratory tests, including re-tests due to laboratory abnormalities and laboratory tests performed at unscheduled visits.

Exceptional circumstances that may require recording of local laboratory results (with corresponding normal ranges) include hospitalization of the study participant due to a medical emergency and missing central laboratory results from a scheduled or unscheduled visit.

If two or more consecutive central laboratory samples are lost or cannot be analyzed for whatever reason, the investigator/delegate will collect an additional sample as soon as possible for repeat analysis, unless a local laboratory sample was collected within the same time window and these test results are available.

Under specific circumstances (e.g., if the study participant lives far from the site and cannot return every month), laboratory samples may be collected at a laboratory close to where the study participant lives (satellite laboratory) and sent to the central laboratory for analysis. In such a case, the satellite laboratory must be provided with the central laboratory sampling kits. Shipment of the samples will be organized by the satellite laboratory. The supervision of the satellite laboratory remains the responsibility of the PI.

Central laboratory reports will be sent to the investigator. In the event of specific (pre-defined) laboratory abnormalities, the central laboratory will alert the sponsor personnel and the concerned site personnel. Alert flags that will trigger such notifications will be displayed in the laboratory manual.

All laboratory reports must be printed, reviewed, signed and dated by the investigator or delegate within 5 calendar days, and filed with the hospital chart. The investigator/delegate must indicate on the laboratory report whether abnormal values are considered clinically relevant or not. Clinically relevant laboratory findings that are known at the time of signing of the ICF must be recorded as medical history in the eCRF.

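### SAP 7.3 keeps local-laboratory values out of the liver counts, and its combined ALT/AST–bilirubin row misses some sequential rises; a flagged supplementary count would close both gaps

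*SAP*

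**What the plan says.** SAP 7.3 sets the data source in its opening line: "Laboratory analyses are based on data received from the central laboratory". Local values are handled apart: "Any local laboratory data collected will be listed separately". Central re-tests and unscheduled samples do count in the summaries.

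The elevated-liver table is limited in period, "Elevated liver parameters during the treatment period will be summarized", and in unit: participants "meeting the criteria defined below within a given central laboratory sample will be tabulated by treatment group". One of its rows combines ALT or AST > 3 × ULN with bilirubin > 2 × ULN. Its percentages use participants with at least one post-baseline value for every listed parameter.

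A separate Hy's Law table adds ALP < 2 × ULN to those two limits. Its only rule is: "This will include study participants meeting all the following criteria". It names no sample rule, window or period.

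Protocol 7.2.5.4 says that the exceptional circumstances which may call for "recording of local laboratory results (with corresponding normal ranges) include hospitalization of the study participant due to a medical emergency"; a second case is a missing central result. If two or more consecutive central samples are lost, an extra sample is collected unless a local result from the same window is available. Samples drawn at a satellite laboratory are analysed centrally.

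Protocol 5.9.1.3 has aminotransferases, bilirubin and alkaline phosphatase tested together after an elevation. Once treatment is stopped, these "must be monitored at least once every 7 calendar days after study treatment discontinuation until" recovery.

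**The concern.** The protocol provides for local testing partly because a participant may be acutely ill in another hospital or have no usable central result. Those are situations in which a liver abnormality matters, yet the values can appear only in a listing. The liver criteria are multiples of ULN and the protocol has the local range recorded, so the values could be put on the same scale.

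The combined row raises a second question. Protocol 5.9.1.3 follows liver tests over time and speaks of a bilirubin increase associated with the aminotransferase rise, without asking for both in one sample. The combined row asks for exactly that, and only within the treatment period.

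At stake is a zero in a liver table that does not mean what it appears to mean. The protocol commits to monitoring liver variables, and earlier human experience is limited to healthy subjects. No efficacy result depends on this.

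**Working it through.** The documents attach no expected count or rate to the liver tables, so there is no planned figure to reproduce. The check is a reading of the rules, one invented participant, and an interval for scale.

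**1. Local values.** SAP 7.3 admits central data to analyses and sends local data to a listing. Protocol 7.2.5.4 allows a local result to stand in for the repeat sample after consecutive lost central samples. In that case the local result may be the only value for the window, and it counts in no liver table. A participant with no central post-baseline value also leaves the denominator of the elevated-liver table.

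**2. Sequential rise.** Invented values in multiples of ULN, all from central samples in the treatment period:

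| Sample | ALT | Bilirubin | ALP |
|---|---|---|---|
| 1 | 1.0 | 0.8 | 0.9 |
| 2 | 4.2 | 1.2 | 1.1 |
| 3 | 2.4 | 2.3 | 1.2 |

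| Count | Result |
|---|---|
| ALT or AST > 3 × ULN | counted (sample 2) |
| Bilirubin > 2 × ULN | counted (sample 3) |
| Combined row, same sample | not counted |
| Hy's Law table, criteria met at any time | counted |
| Hy's Law table, if the same-sample rule is carried over | not counted |

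Had ALT still been above 3 × ULN in sample 3, the combined row would have counted this participant. The omission therefore needs ALT/AST to have fallen to 3 × ULN or below first.

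**3. Period.** SAP 11.2 ends the treatment period at EOT or, for premature discontinuers without an EOT date, at the treatment end date. The protocol places a premature EOT visit 1 to 5 days after the last dose. By schedule the period thus closes no later than day 5 after the last dose, whereas the first weekly monitoring sample may come as late as day 7. A bilirubin rise seen only in that monitoring falls outside the elevated-liver table whatever the sample rule.

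End-of-Study is 10 ± 3 days after EOT. For a premature discontinuer that is 1 + 7 = 8 to 5 + 13 = 18 days after the last dose. At exact 7-day spacing (days 7 and 14), one or two monitoring samples precede it.

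**4. Scale only.** Assume 60 treated per arm (Protocol 9.4 plans 60 per arm) and one omitted participant.

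- 0/60: two-sided exact 95% interval 0 to 1 − 0.025^(1/60) = 6.0%; one-sided 95% upper limit 1 − 0.05^(1/60) = 4.9%.
- 1/60 = 1.7%: two-sided exact 95% interval 0.04% to 8.9%; one-sided 95% upper limit, the 0.95 quantile of Beta(2, 59), 7.7%.

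**The case against.** Tabulating one standardised source and listing the rest is a transparent, pre-specified choice. Protocol-mandated tests, including re-tests and unscheduled visits, go to the central laboratory, satellite samples are analysed there, and local results are for exceptional circumstances. A hospitalised participant's central samples still count. In-patient hospitalisation for an adverse event makes it serious, and liver abnormalities that lead to discontinuation must be reported as adverse events, so such a case should surface in the AE or SAE tables. A sequential riser within the treatment period also appears in the single-parameter rows, and central values feed the marked-abnormality and shift tables. Laboratory abnormalities are summarised descriptively, the adverse event of special interest is somnolence, and Phase 1 hepatic variables were unaffected. All of this stands, and it limits the point to how a few liver rows are counted.

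Three stronger readings are tempting and not supported:

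- *The Hy's Law table excludes sequential rises.* The same-sample wording belongs to the elevated-liver table. Read literally, the Hy's Law table could count them; its timing is simply not stated.
- *Any bilirubin rise a week after the ALT peak is missed.* Aminotransferases and bilirubin are re-tested together, so the combined row misses it only if ALT/AST is no longer above 3 × ULN or the sample lies outside the treatment period.
- *Liver events in hospitalised participants are lost.* Their local values are listed and the events can reach the AE/SAE tables; they are absent only from the laboratory counts.

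None of this answers the narrower point: the rows a reader would consult for a combined liver signal can omit a participant who had one, and the Hy's Law table can be programmed in two ways.

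**Conclusion.** The point holds in limited form. By rule, local values enter no liver count. The combined row of the elevated-liver table omits a participant whose bilirubin crosses 2 × ULN only after ALT/AST has fallen to 3 × ULN or below, or only in post-discontinuation monitoring. For the Hy's Law table the gap is a missing definition, not a demonstrated exclusion.

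The size cannot be estimated, because the documents give no rate of liver events, local tests or sequential rises. The contrast of 0/60 with 1/60 assumes one omitted case and shows only how much a single participant matters at this sample size. This is an inexpensive improvement to a descriptive safety display; the primary analysis is unaffected.

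**What to change.** Keep the planned central, same-sample count in SAP 7.3. For both the elevated-liver and Hy's Law tables, add beside it a flagged supplementary count that:

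1. includes local values, expressed as multiples of their own recorded ULN, where value and range are available;
2. counts bilirubin > 2 × ULN in the same sample as, or any sample after, ALT or AST > 3 × ULN, within a window whose length the SAP fixes before unblinding;
3. covers all post-baseline samples up to End-of-Study, including post-discontinuation monitoring.

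State in the same place which timing rule and period apply to the planned Hy's Law table. Monitoring that continues past End-of-Study would still fall outside the supplementary count, and a footnote should say so.

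The cost is a few lines of SAP text and modest programming. The protocol provides for recording local results with ranges but does not say that all four liver parameters will be available, so the supplementary count may be incomplete. The downside is mixed laboratory sources, which ULN scaling and the flag make visible. Nothing in the current plan is lost.

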7.4 Electrocardiography

ECG analyses are based on data received from the central reader. Unless noted otherwise, ECG summaries and listings will include scheduled, re-test, and unscheduled assessments.

Descriptive summary statistics for each scheduled visit (re-test excluded) will be provided for observed values and change from baseline in ECG parameters (QT, QRS, QT corrected according to Fridericia's formula, QT corrected according to Bazett's formula, heart rate, and PR interval).

Marked ECG abnormalities are defined in Table 4. The number (%) of study participants with a marked ECG abnormality will be provided for each ECG parameter.

Percentages will be based on the number of participants having at least one post-baseline value for criteria based on post-baseline values only, or those having a baseline value and at least one post-baseline value per ECG parameter for criteria based on change from baseline. For non-mutually exclusive criteria (i.e., HR, PR and QRS), a subject will be counted only once in case of multiple occurrences but may be reported in more than one marked ECG abnormality criterion of a given parameter. For mutually exclusive criteria (i.e., QTc), only the subject's worst post-baseline value (or worst change from baseline value) will be counted.

ECG findings during the treatment period will be summarized separately and listed. ECG abnormality categories and findings will be sorted by descending frequency, first in the ACT-539313 treatment group and then in the placebo group. After this sorting, ECG

ACT-539313		Statistical Analysis Plan
ID-082A201		for Clinical Study Report
1 April 2022, page 35/60	Confidential	Version 3
		Doc No D-22,100

abnormality categories will be presented in alphabetical order with ECG finding sorted within ECG abnormality category in alphabetical order. All ECG values for study participants with at least one marked ECG abnormality during the treatment period will be listed.

ECG parameter	Criteria for marked ECG abnormalities	
QTcF, QTcB (ms)	$> 450 \text{ and} \le 480$	
	$> 480 \text{ and} \le 500$	
	> 500	
	$>$ 30 and \leq 60 increase from baseline	
	> 60 increase from baseline	
HR (bpm)	< 45	
	< 50	
	> 10 and ≤ 20 decrease from baseline	
	> 20 decrease from baseline	
PR (ms)	> 200	
QRS (ms)	> 110	

Table 4Marked abnormalities in ECG parameters

bpm = beats per minute; ECG = electrocardiogram; HR = heart rate; QTcB = QT interval corrected according to Bazett's formula; QTcF = QT interval corrected according to Fridericia's formula.

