	• Occurrence of suicidal ideation and/or behavior while on study treatment based on the C-SSRS © from baseline to all assessed time points during the study up to EOS.		
Other exploratory objectives			
To assess the PK of ACT-539313	• ACT-539313 plasma concentrations prior to morning dosing at Week 4, Week 8, and Week 12.		

a A treatment-emergent AE is any AE temporally associated with the use of study treatment (from study treatment start up to EOS, whether or not considered by the investigator as related to study treatment).

b A treatment-emergent marked laboratory abnormality or medically relevant ECG abnormality is any marked laboratory abnormality or medically relevant ECG abnormality temporally associated with the use of study treatment (from study treatment start to all assessed time points during the study). The selection of marked/medically relevant abnormalities considered for the analyses will be based on standard definitions and described in the SAP.

AE = adverse event; AESI = adverse event of special interest; BE = binge eating; BED = binge eating disorder; CGI-C = Clinical Global Impression of Change scale; CGI-S = Clinical Global Impression of Severity scale ; C-SSRS© = Columbia Suicide Severity Rating Scale; ECG = electrocardiogram; EDE-Q7 = Eating Disorder Examination Questionnaire (7-item); EOS = End-of-Study; EOT = End-of-Treatment; HAMD-17 = Hamilton Rating Scale for Depression (17-item); FERT = Facial Expression Recognition Task; HbA1c = glycated hemoglobin; MPS = Maier-Philipp subscale; PGI-C = Patient Global Impression of Severity; PT = preferred term; SAE = serious adverse event; SAP = statistical analysis plan; SSS = Stanford Sleepiness Scale: TEAE = treatment-emergent adverse event; YBOCS-BE = Yale-Brown Obsessive-Compulsive Scale modified for Binge Eating

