# 9.2.9 Electrocardiography

Descriptive summary statistics by visit and study treatment will be provided for observed treatment-emergent values and changes from baseline in numeric 12-lead ECG values (HR, and the intervals PR, QRS, QT, QTcB, and QTcF).

Treatment-emergent marked abnormalities for 12-lead ECG variables will be summarized at all visits.

In addition, morphological ECG abnormalities that were not present before first study treatment intake (using data from the ECG provider) will be summarized.

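### SAP 7.4 drops, without declaring it, the protocol's condition that summarised morphological ECG abnormalities be absent before first dose, so unchanged pre-existing findings enter the on-treatment table

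*SAP*

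**What the plan says.** For qualitative ECG findings, Protocol 9.2.9 plans to summarise "morphological ECG abnormalities that were not present before first study treatment intake". SAP 7.4 plans instead that "ECG findings during the treatment period will be summarized separately and listed", with no reference to the pre-treatment ECG.

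For numeric ECG criteria, Protocol 9.2.9 states: "Treatment-emergent marked abnormalities for 12-lead ECG variables will be summarized at all visits". SAP 7.4 states: "The number (%) of study participants with a marked ECG abnormality will be provided for each ECG parameter". For laboratory values, SAP 7.3 states: "The number (%) of participants with treatment-emergent marked laboratory abnormalities will be tabulated".

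The only definition of treatment-emergent for laboratory and ECG abnormalities is in Protocol Table 2, footnote b: the abnormality must be "temporally associated with the use of study treatment (from study treatment start to all assessed time points during the study"). It makes no comparison with baseline. SAP 7.1 limits safety tables to treatment-emergent data unless noted otherwise, but gives no rule for laboratory or ECG data. For adverse events, SAP 7.2 does require onset or worsening after treatment start.

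SAP 12.1 declares one change from the protocol, the analysis set for demographics and disease characteristics. Sections 12.2 to 12.4 are marked not applicable.

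**The concern.** A table of ECG findings during treatment is read as showing what appeared on treatment. If it also holds conduction or morphology findings already present at screening, the reader cannot tell new from old without going through the listing. The protocol had guarded against this for qualitative findings, and the SAP removes the guard without saying so.

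The marked-abnormality tables raise a similar question. A participant above an absolute cut-off at baseline and unchanged on treatment is counted beside one who crossed it on treatment. Marked laboratory abnormalities and medically relevant ECG abnormalities are both named safety endpoints. Eligibility does not screen all such participants out: exclusion criteria 10 and 11 (ECG and general laboratory findings) rest on investigator opinion, and no criterion sets a limit for PR, QRS, heart rate, GFR or lipids.

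**Working it through.** The main check compares texts; the arithmetic only illustrates size.

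**1. Does another SAP rule restore the dropped condition?** The candidate is SAP 7.1, which restricts tables to treatment-emergent data. The only definition of that term for ECG is footnote b, which is a timing rule. The SAP 7.4 sentence is already limited to the treatment period, so adding SAP 7.1 changes nothing. The protocol condition can be applied, because Protocol 7.2.5.3 schedules an ECG at screening as well as at end of treatment.

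**2. Trace four cases.**
- Conduction finding at screening, identical at end of treatment: not summarised under Protocol 9.2.9; summarised under SAP 7.4. The documents differ.
- PR above 200 ms at screening and unchanged: counted under footnote b and under SAP 7.4. The documents agree, but the count does not separate old from new.
- QTc unchanged from baseline: not counted under the two QTc-increase rows of SAP Table 4.
- Baseline creatinine above ULN and unchanged: not counted on creatinine, because that row of Tables 13 and 14 is referenced to baseline. If the same participant's GFR is below 60 throughout, he or she is counted on GFR.

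**3. How far does the second gap reach?** SAP Table 4 has 5 QTc criteria, 4 heart-rate criteria, 1 PR and 1 QRS: 5 + 4 + 1 + 1 = 11. Of these, 2 QTc increases and 2 heart-rate decreases are changes from baseline, 2 + 2 = 4. That leaves 11 − 4 = 7 absolute criteria. In Tables 11 to 14, high hemoglobin and creatinine (each with baseline above ULN) and INR on anticoagulants are baseline-referenced. Affected examples are PR > 200, QRS > 110, QTc > 450, HR < 50, GFR < 60, total cholesterol > 7 mmol/L and triglycerides > 5.7 mmol/L. For absolute criteria, SAP 7.3 and 7.4 use as denominator participants with at least one post-baseline value, so a baseline value is not even required.

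**4. Illustrative size.** Inputs: 60 participants per arm (Protocol 9.4) and an assumed proportion b who carry a given finding through unchanged. The documents give no value for b.
- Expected carried-in count per arm = 60 × b: 60 × 0.02 = 1.2; 60 × 0.05 = 3; 60 × 0.10 = 6.
- SE of the chance difference between arms = √(2b(1 − b)/60): √(2 × 0.02 × 0.98/60) = 0.026; √(2 × 0.05 × 0.95/60) = 0.040; √(2 × 0.10 × 0.90/60) = 0.055. That is 2.6, 4.0 and 5.5 percentage points.

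If n₁ and n₀ are the proportions of each arm with a new finding, the table shows b + n₁ against b + n₀. The expected difference is still n₁ − n₀, but the ratio (b + n₁)/(b + n₀) is pulled towards 1, and the observed difference picks up the chance imbalance in b.

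**The case against.** The strongest reply is that timing-only emergence for marked values is the protocol's own pre-specified rule, which the SAP follows. SAP 7.4 says openly that some criteria rest on post-baseline values only and gives the matching denominator. This stands. A reader might infer that the SAP departs from the protocol across all its marked laboratory and ECG tables, or that none of the cut-offs looks at baseline. Neither is supported: the one SAP departure that adds unchanged pre-existing findings is the dropped condition for morphological findings, and several rows are baseline-referenced.

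Second, new or worsened findings appear elsewhere. Protocol 8.1.1 makes clinically significant ECG and laboratory findings adverse events when new or worsened. Change from baseline is summarised for ECG, hematology and chemistry. Shift tables cover some liver, lipid and hematology parameters, and all values are listed for participants with a marked abnormality. This softens the consequence but does not correct the count. The shift tables use normal ranges rather than the marked thresholds, and they omit ECG, glucose and renal function.

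Third, the size is speculative. The prevalences are assumptions, the SE is the ordinary binomial one for any rate at 60 per arm, and randomisation balances pre-existing findings in expectation. Exclusion of AST, ALT or bilirubin above 1.5 × ULN makes pre-existing marked liver values unlikely. All of this stands.

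Fourth, counting only criteria unmet at baseline or met at a worse level would hide real worsening. PR and QRS have one level, and cholesterol and triglycerides have no second high level. Someone already above such a cut-off could rise much further and never be counted. This also stands and shapes the fix.

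**Conclusion.** The point holds in two parts of different weight. The firm part is that SAP 7.4 omits a condition set in Protocol 9.2.9, no other SAP rule restores it, and Section 12 does not declare it. Followed as written, the SAP counts unchanged pre-existing morphological findings in the on-treatment summary.

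The lesser part concerns marked laboratory and ECG criteria with absolute cut-offs. The protocol's definition lets in participants who met the cut-off at baseline. The SAP leaves that gap open but did not create it, so this is a matter of making the table readable, not of correcting an error against the protocol. It does not reach the change-from-baseline criteria or the baseline-referenced high hemoglobin, creatinine and INR rows.

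The consequence is limited to descriptive safety tables: inflated counts in both arms, a diluted contrast and some chance imbalance. A reader might infer that the safety tables are biased towards or against the drug. The documents do not support that, since allocation is randomised and carried-in findings are expected equally in both arms. The 1.2 to 6 per arm rests wholly on the assumed 2% to 10%.

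**What to change.** - **SAP 7.4, ECG findings:** restrict the summary to findings not present on any pre-treatment ECG, as Protocol 9.2.9 requires, and keep all findings in the listing. If the sponsor prefers the wider summary, declare it in SAP 12.1 with a reason.
- **SAP 7.3 and 7.4, absolute cut-offs:** keep the count that follows from footnote b, but show it split by whether the same criterion was met at baseline, with a category for baseline missing. Do not drop participants who met it at baseline. This leaves the protocol definition intact, and the split can be recorded in SAP 12.4 as an additional display.
- **No change** to the change-from-baseline criteria or the baseline-referenced rows.

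The cost is a few sentences in the SAP, a pre-treatment condition for the ECG findings table and a baseline flag in the marked-abnormality tables. The screening ECG and screening laboratory tests are already scheduled, so no new data are needed.
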